Shared Session 1: Screening. During Session 1 participants will be screened for the study with the rTMS screening forms (demographics, health, etc.), BIAC screening form, and a urine test. If they pass the screening procedure, they will proceed to the to the TMS Service Center, where motor threshold will be defined; and where they will learn and practice the motion tasks used in the study (about 0.5 hr) during visual cortex stimulation in order to acclimate them to rTMS and to obtain phosphene, motion disruption thresholds, for future dosing of rTMS. The motion task in the screening visit will consist of the second phase (motion period) of the task described below.

Shared Session 2: MRI Scanning. During Session 2 (2 hrs), participants undergo a 60-min MRI session. At BIAC, after obtaining a structural MRI and DTI and resting-state fMRI scans, fMRI data will be recorded from subjects while they perform the Motion task. BOLD images will be acquired with a 3.0T GE MR Scanner. Stimuli will be back-projected onto a screen located at the head of the MRI bed using an LCD projector. Subjects will view the screen via a mirror system located in the head coil. Task onset will be electronically synchronized with the MRI acquisition computer.

Shared Motion Task: All three Studies use the same motion task but manipulate different factors. Every trial consists of three phases (**Fig. 1A**): stimulation, motion, and inter-trial interval. Here we describe the task with rTMS—practice versions and fMRI versions of the Motion Task are identical, minus the delivery of rTMS.

1. Stimulation period (3 s).

Subjects view two circles on either side of fixation, each filled with stationary random dots, while receiving rTMS to right MT or vertex. When an rTMS burst is briefer than 3 s, its onset is delayed so it co-terminates with the stimulation period (e.g., a 1.5-s rTMS burst is delayed by 1.5 s). rTMS is delivered to MT at a value not to exceed 120% of

individualized motor threshold, an intensity that yields both inhibitory and excitatory effects for brief trains (Gerschlager et al., 2001; Modugno et al., 2001; Fitzgerald et al., 2002; Lang et al., 2006) and has been shown to be within the published safety guidelines (Rossi et al., 2009b).

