2. *Motion period (3 s)*. The dots inside both circles start moving. All dots in the right circle move randomly in all directions (0% coherence—COH). Most dots in the left circle move randomly, but a percentage of dots move upward or downward together. The percentage of dots moving together is either high (18% coherence) or low (3% coherence) to make the task easy or hard (~90% or 60% correct, respectively, where chance=50%) as established in our pilot studies (Britten et al., 1992). Subjects indicate as quickly as possible whether the coherently moving dots in the left circle moved upwards or downwards through responses on two different buttons. Dot motion continues for 3 s regardless of response time. After the motion period, feedback for correct vs. incorrect responses is delivered: high- vs. low-pitch sounds (corresponding to high vs. low monetary payoffs at the end of the study).

3. *Inter-trial interval (ITI, mean: 4 s)*. Subjects maintain fixation on a central cross for a period varying between 2 and 7 sec (mean: 4 sec). This jittered ITI is critical for event-related fMRI analyses, but is also used to keep conditions identical.

Phosphene Threshold Determination: All rTMS procedures will occur in rooms 54210, 54211 and 54212 in the Department of Psychiatry and Behavioral Sciences, Duke Clinic South. Phosphene threshold is defined as the minimum magnetic flux needed to elicit phosphenes (the perception of moving lights in the absence of an actual visual stimulus) in 5 out of 10 trials. Like the motor threshold, phosphene threshold is a standard approach for determining the intensity of rTMS for each individual to reduce seizure risk. The phosphene threshold will be determined in a dark room using a blindfold to enhance the subject's ability to detect phosphenes. The presence of moving phosphenes will be identified by subject verbal response. The scalp region producing moving phosphenes will be identified and recorded on the BrainSight neuronavigation system. Phosphene and motion disruption threshold will be used to determine the exact location in V5 which is involved in motion perception; then intensity of stimulation over this specific area will be defined according to rMT. From this, we will confirm the target engagement.

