Motor Threshold Determination: Motor threshold (MT) is defined as the minimum magnetic flux needed to elicit a threshold EMG response in a target muscle in 5 out of 10 trials. MT is the standard in the field for determining the intensity of rTMS for each individual to reduce seizure risk. The motor evoked potentials (MEP) for the contralateral first dorsal interosseus (FDI) will be measured with EMG. The scalp region producing the largest amplitude MEP will be identified and recorded on the BrainSight neuronavigation system. At that scalp location, the lowest rTMS intensity able to elicit 5 MEP's of $\geq 50\mu\text{V}$ in peak-to-peak amplitude in 10 trials at this site will be determined, using a descending method-of-limits procedure. MT will be determined for each hemisphere with the muscle at rest (verified by baseline EMG). Individual MT will be used to determine the intensity of stimulation for each individual, as recommended by safety guidelines.

Concurrent TMS-fMRI Procedure. The TMS coil is positioned over the individual's marked right MT target site and locked into place using a coil holder (MagVenture). Subjects are then positioned in the bore of the MR scanner. Several interleaved TMS-fMRI runs are then performed. In each run, rTMS bursts are delivered on each trial (**Fig. 1B**) at a value not to exceed to 120% of the motor threshold. fMRI is acquired using a gradient echo sequence with the following imaging parameters: flip angle=77°,

TR=1750ms, TE=27ms, FOV=25.6 mm², and 39 4mm thick slices. These data are collected with a GE three-axis balanced-torque head gradient coil and a shielded end-capped quadrature transmit-receive birdcage radio frequency coil. A delay of 250 ms is inserted between each acquisition during which a single biphasic TMS pulse is delivered. To track the actual position of the coil during stimulation, four fiducial markers are placed on the coil. rTMS administration will be controlled by an external computer and will be time-locked relative to stimulus presentation. After the concurrent TMS-fMRI Session, a brief rTMS side effect rating scale and visual analog mood ratings will be administered before and after each rTMS block.

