Study 1 investigates the effects of **frequency** and number of pulses, manipulated across blocks. Table 2 describes the 7 conditions used in this experiment. rTMS is applied to MT or the vertex at 7 doses consisting of up to 30 pulses at 1, 5, or 10Hz. In conditions 1–3, these frequencies are delivered for 3 seconds leading to 3, 15, and 30 pulses, respectively. In conditions 4 and 5, frequency remains at 10Hz, but durations are 1.5 and .3 seconds, respectively, to yield

Table 2. Conditions in Study 1

Cond	Sites	Hz	Sec.	Pulses
1	MT	1	3.0	3
2	MT	5	3.0	15
3	MT	10	3.0	30
4	MT	10	1.5	15
5	MT	10	0.3	3
6	Vtx	1	3.0	3
7	Vtx	10	3.0	30

numbers of pulses that match conditions 1 and 2. Thus, we manipulate frequency while keeping duration constant, and number of pulses while keeping frequency constant. In control vertex stimulation conditions 6 and 7, rTMS is delivered for 3 seconds at 1Hz or 10Hz, matching the pulses of conditions 1 and 3, respectively.

Each of the 7 conditions is assigned to two blocks of 20 trials each (40 trials/condition); each trial lasts 10 seconds, and we will administer 14 blocks (47 minutes, 280 trials total) in both the TMS-fMRI and TMS-EEG experiments. The TMS-fMRI and TMS-EEG will necessitate 60 minutes preparation to adjust the positioning for the TMS coil and—in the TMS—EEG experiment—apply the EEG cap, as well as 30 minutes for a brief rTMS side effect rating scale and visual analog mood ratings will be administered before and after each rTMS block. Thus, the entire session will last 3 hours for both the TMS-fMRI and TMS-EEG Session. As above, subjects' side effects will be monitored closely, and all side effect monitoring described above will be repeated. Furthermore, all intensities fall within the rTMS safety guidelines (Rossi et al., 2009b).

Study 2

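### The TMS-fMRI procedure allows one pulse per 250-ms gap between acquisitions; if that sentence governs, the 5 Hz and 10 Hz trains of Studies 1 to 3 cannot be delivered in the scanner

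*Combined protocol and SAP*

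**What the plan says.** The Concurrent TMS-fMRI Procedure (section 4) gives the sequence as "TR=1750ms, TE=27ms" with 39 slices, then adds: "A delay of 250 ms is inserted between each acquisition during which a single biphasic TMS pulse is delivered". It does not say whether an acquisition is a volume or a slice, or whether the delay lies inside the TR or is added to it.

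The same paragraph says "In each run, rTMS bursts are delivered on each trial", citing Fig. 1B, and "rTMS administration will be controlled by an external computer and will be time-locked relative to stimulus presentation".

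The Shared Motion Task sets a 3-s stimulation period and says of shorter bursts: "When an rTMS burst is briefer than 3 s, its onset is delayed so it co-terminates with the stimulation period".

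Study 1 sets the doses: "In conditions 1–3, these frequencies are delivered for 3 seconds leading to 3, 15, and 30 pulses, respectively". Conditions 4 and 5 are 10 Hz for 1.5 s and 0.3 s (15 and 3 pulses). Conditions 6 and 7 repeat conditions 1 and 3 at the vertex. These apply in the scanner too: "we will administer 14 blocks (47 minutes, 280 trials total) in both the TMS-fMRI and TMS-EEG experiments".

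The Study 3 text says that Studies 2 and 3 use 5 Hz only, and both studies also run in TMS-fMRI.

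**The concern.** The one-pulse sentence and the dose table describe different stimulation in the same session. What differs is the experimental variable itself. The primary objective concerns frequency and number of pulses, and the primary endpoint (section 2) makes predictions for MT activity in fMRI as well as EEG.

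Two outcomes are possible:

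- **The sentence is followed.** With one gap per volume, conditions 1, 2 and 3 all shrink to one or two pulses per trial. In fMRI, 1, 5 and 10 Hz are then no longer different treatments.
- **The dose table is followed.** The trains are delivered, but the sentence no longer describes how pulses are kept apart from imaging, so pulses may land during readout. The fMRI analyses paragraph of section 12 lists motion and quality inspection and physiological-noise modelling. It has no step for slices or volumes hit by a pulse.

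**Working it through.** **Inputs.** Gap 0.25 s with one pulse, TR 1.75 s and 39 slices (Concurrent TMS-fMRI Procedure); doses from Table 2; 40 trials per condition (Study 1).

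**The plan's own figures.** Pulses = Hz × seconds reproduces all seven rows of Table 2: 3, 15, 30, 15, 3, 3, 30. The session length also reproduces: 14 × 20 × 10 s = 2,800 s = 46.7 min, stated as 47.

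**Ceiling that does not depend on the meaning of acquisition.** Let imaging take no time, so that gaps run back to back. The rate is at most 1/0.25 = 4 pulses per second, below both 5 and 10 Hz. A train of n pulses at f Hz spans (n − 1)/f seconds, and a span that is not a multiple of 0.25 s touches at most floor(span/0.25) + 2 gaps:

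- Condition 2: 14/5 = 2.8 s, 11 + 2 = 13 of 15.
- Conditions 3 and 7: 29/10 = 2.9 s, 11 + 2 = 13 of 30.
- Condition 4: 14/10 = 1.4 s, 5 + 2 = 7 of 15.
- Condition 5: 2/10 = 0.2 s, 0 + 2 = 2 of 3.
- Conditions 1 and 6: pulses 1 s apart fall in separate gaps, so 3 of 3.

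This is a bound, not a usable scheme.

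**One gap per slice.** 39 × 0.25 s = 9.75 s per volume, which cannot fit a TR of 1.75 s.

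**One gap per volume.** The cycle is T = 1.75 s (delay inside the TR) or 2.0 s (delay added), giving 0.57 or 0.50 pulses per second. The most pulses in a window W, with the pulse anywhere in its gap, is floor((W + 0.25)/T) + 1, apart from the exact-multiple case noted below:

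- W = 3 s: 3.25/1.75 = 1.86 and 3.25/2.0 = 1.63, so 2. The fewest is floor(2.75/T) = 1.
- W = 1.5 s: 1.75/2.0 = 0.88, so 1. At T = 1.75 the ratio is exactly 1, which only touches the edge, so again 1.
- W = 0.3 s: 1.

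| Condition | Site | Hz | s | Required | Ceiling, no imaging time | Most, one gap per volume |
|---|---|---|---|---|---|---|
| 1 | MT | 1 | 3.0 | 3 | 3 | 2 |
| 2 | MT | 5 | 3.0 | 15 | 13 | 2 |
| 3 | MT | 10 | 3.0 | 30 | 13 | 2 |
| 4 | MT | 10 | 1.5 | 15 | 7 | 1 |
| 5 | MT | 10 | 0.3 | 3 | 2 | 1 |
| 6 | Vertex | 1 | 3.0 | 3 | 3 | 2 |
| 7 | Vertex | 10 | 3.0 | 30 | 13 | 2 |

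Per session, Table 2 requires 40 × 99 = 3,960 pulses. One gap per volume allows at most 200 × 2 + 80 × 1 = 480 (12.1%).

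**Studies 2 and 3.** Train length is not stated. With one gap per volume it does not matter: pulses in successive gaps are at least 1.75 − 0.25 = 1.5 s apart (1.75 s if T = 2.0), whereas 5 Hz needs 0.2 s. If 3-s trains are assumed, the zero-imaging-time ceiling of 13 of 15 also applies.

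**The case against.** The strongest reply is that one sentence stands against several that agree with each other: a seven-row dose table, bursts on every trial, and 5 Hz for Studies 2 and 3. Staff are unlikely to ignore all of these, so a wording fault is the natural reading. Fig. 1B, cited for the bursts, is not available and may show a workable scheme. This stands, and it limits the conclusion to a contradiction in the text. It does not remove the contradiction: a figure showing another scheme would still leave a wrong sentence to correct.

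Three stronger inferences are tempting and are not supported:

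- **That 94% of Study 1 stimulation is undeliverable.** Conditions 2, 3, 4, 5 and 7 do carry 40 × 93 = 3,720 of 3,960 pulses. They fail only if the one-pulse sentence governs; if Table 2 governs, all are delivered.
- **That most pulses fall in readout if Table 2 is followed.** Keeping one 250-ms gap per volume would give 1.75/2.0 = 87.5% or 1.5/1.75 = 85.7%. That borrows the gap from the very sentence being set aside.
- **That time-locking to the stimulus, with an interval jittered from 2 to 7 s, rules out alignment with the scanner.** The step size of the jitter is not given, and a 10-s trial equals five 2.0-s cycles. Shared Session 2 also mentions synchronizing task onset with the scanner, though only for that session.

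**Conclusion.** The plan is wrong as written on this point, not merely short of detail. If the one-pulse sentence governs, Study 1 conditions 2, 3, 4, 5 and 7 fail under any meaning of acquisition, and the 5 Hz trains of Studies 2 and 3 fail with them (on the zero-imaging-time bound, assuming 3-s trains). With one gap per volume, the 1 Hz trains fail as well (at most 2 of 3 pulses), and the fMRI contrasts of frequency and pulse number collapse.

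It is likelier that the sentence is the error. The remaining problem is then possible overlap with readout, of a size the text does not determine, and no analysis step to handle it. That is a risk of artefact or data loss, not a demonstrated bias, and it disappears if the real timing keeps pulses out of readout. The documents do not show which scheme was run.

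The TMS-EEG sessions with their reaction times, the Session 2 fMRI without TMS, and the pilot sessions without MRI are not affected.

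**What to change.** 1. Correct the one-pulse sentence so that the stated TMS-fMRI timing delivers the Table 2 trains and the 5 Hz trains of Studies 2 and 3. List pulses per trial by condition, including the train length in Studies 2 and 3.
2. Build the first-level fMRI regressors from logged pulse times, which the external control computer could record. If any pulses overlap readout, exclude or model the affected slices under a rule fixed in the SAP.
3. Limit fMRI conclusions on frequency and pulse number to conditions whose specified train is delivered in the scanner.

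**Cost.** If the sentence is a wording fault, the changes are to text and analysis only. If pulses also overlap readout, some fMRI data are lost: excluding by time costs at most about 3 s of each 10-s trial (30%) for a 3-s train, and dropping whole volumes costs more. If the one-pulse timing is real, either the acquisition timing must be revised, which is more than a text change, or item 3 must be accepted with its narrower claims.

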Research Protocol Summary

1. Protocol Title: Effects of rTMS on human brain activity measured with EEG and fMRI

Note: This protocol covers three studies (Aims 1-3) of a NIMH BRAIN R01 grant supporting this research currently under review.

2. Purpose of the Study:

Treating psychiatric and motor disorders without surgery or life-long pharmacology is a vexing but attainable goal. One avenue of progress has been the development of non-invasive brain stimulation methods such as repetitive transcranial magnetic stimulation (rTMS). This project investigates the effects of rTMS on neural circuits as a function of spatiotemporal parameters and brain state in order to better understand why the method works and how to improve its efficacy. Leveraging our expertise in application of TMS methodology during concurrent single neuron recording techniques in non-human primates and imaging and scalp potential techniques in humans (fMRI and EEG), we aim to resolve three interlocking problems in the design and application of rTMS: **stimulation frequency, spatial targeting, and interactions with brain state.**

Primary Objective: Investigate rTMS temporal parameters: impact of frequency (1Hz versus 5Hz versus 10Hz rTMS) and number of pulses.

Primary Endpoint: We make 2 general predictions. **(1)** 1Hz vs. 5/10Hz rTMS will have inhibitory vs. excitatory effects on behavior (reaction times—RTs) and motion-related (high vs low coherence) medial temporal (MT) activity (in both EEG, and fMRI). **(2)** Excitatory effects for 10Hz will increase with number of pulses.

Secondary Objective: Examine rTMS spatial targeting: recruitment of specific networks in either dorsal (rTMS-D) or ventral (rTMS-V) pathways.

Secondary Endpoint: We predict that compared to the control condition, rTMS-D will enhance motion task performance and motion-related (high vs. low coherence) activity in the dorsal pathway (e.g., FEF, IPS), whereas rTMS-V will enhance motion-related activity in ventral pathway, with little or no effect on motion task performance.

Tertiary Objective: Establish rTMS brain state-dependency: stimulation of active versus inactive regions.

Tertiary Endpoint: We predict that rTMS effects on MT activity will be potentiated during motion task blocks compared to both color task and rest blocks.

3. Background & Significance:

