The study procedures outlined below cover 3 integrated experiments. A general overview of each study suggests a highly integrated set of experiments that will help explain neuromodulatory effects. **Study 1** investigates the effects of **frequency** and number of pulses, manipulated across blocks. rTMS is applied to MT or the vertex at 7 doses consisting of up to 30 pulses at 1, 5, or 10Hz. **Study 2** manipulates the **location** and orientation of the coil during rTMS of MT to bias rTMS effects either toward the dorsal pathway or toward the ventral pathway. **Study 3** manipulates **brain state** and uses *motion task blocks*, as in Studies 1 and 2, but also *color task blocks* and *rest blocks*. As in Study 2, only 5Hz rTMS is used. Therefore, we describe first the *shared* design information, and then describe design information *specific* to each of the 3 Studies.

Table 1. TIMELINE OF STUDY PROCEDURES:

Assessment	Screening Session	Session 1 (Shared)	Session 2 or 3 TMS-fMRI	Session 2 or 3 TMS-EEG
1. Subject consent & questionnaires	X			
2. Urine Test	X			
3. Practice with Motion task	X			
4. TMS Tolerability	X			
5. TMS Motion disruption, phosphene and motor thresholds	X			
6. Structural MRI (T1 & DWI)		X		
7. Resting-state fMRI		X		
8. Event-related fMRI with Motion task		X		
9. Concurrent TMS-fMRI with Motion task			X	
10. Concurrent TMS-EEG with Motion task				X
11. Side Effect Checklist	X		X	X

The Table above presents the timeline of major study procedures.

Shared Design Details

Subject Screening. In each of the 3 studies proposed, 48 different healthy young adults (18-30 y.o.) will participate in both TMS-MRI and TMS-EEG components of each study. Participants will have no psychiatric or neurological history and no ongoing psychoactive drug use (for more details see Section 5 below). Normal right-handed volunteers will be recruited from the community.

Each participant will take part in up to **seven** sessions: the first two sessions are *shared* by the TMS-MRI and TMS-EEG components of each study. The third and fourth sessions correspond separately to the TMS-fMRI and TMS-EEG sessions—with designs specific to each of the 3 Experiments—with the order counterbalanced across participants. If participants have been included in the pilot protocol, they will have two additional visits. Finally, an additional visit is built in if subjects need to make up a visit (e.g. poor task performance).

[figure not shown]

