Study 2 manipulates the location and orientation of the coil during rTMS of MT to bias rTMS effects either *toward the dorsal pathway (rTMS-D)* or *toward the ventral pathway (rTMS-V)*. Positioning parameters are chosen by integrating information about (1) white-matter connectivity for ventral/dorsal pathways from MT, and (2) the induced E-field from MRI-based individual head models and its relationship to functional activity. First, fMRI maps are used to select the stimulation site, which is the seed point for E-field estimation. Next, DWI tractography estimates from the stimulation site, MT, are used to define trajectories of fiber tracts from MT into the dorsal pathway, specifically to FEF, or into the ventral pathway, specifically to the anterior temporal lobe. Then, structural scans (T1- and T2-weighted) are used for E-field modeling to select the best coil orientations for aligning the E-field distribution along the dorsal or ventral pathways identified above on an individual basis.

Thus, Study 2 uses 3 spatial conditions for rTMS stimulation. Each of the 3 conditions is assigned to four blocks of 20 trials each (80 trials/condition); each trial lasts 10 seconds, and we will administer 12 blocks (40 minutes, 240 trials total) in both the TMS-fMRI and TMS-EEG experiments. The TMS-fMRI and TMS-EEG will necessitate 60 minutes preparation to adjust the positioning for the TMS coil and—in the TMS—EEG experiment—apply the EEG cap, as well as 30 minutes for a brief rTMS side effect rating scale and visual analog mood ratings will be administered before and after each rTMS block. Thus, the entire session will last 3 hours for both the TMS-fMRI and TMS-EEG Session. As above, subjects' side effects will be monitored closely.

Study 3

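### Study 2 never defines the control in its secondary endpoint; against vertex, a general 5Hz MT effect could pass as a pathway effect, and no direct rTMS-D versus rTMS-V test is planned

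*Combined protocol and SAP*

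**What the plan says.** The secondary endpoint (section 2) has two limbs. The dorsal limb is that "compared to the control condition, rTMS-D will enhance motion task performance and motion-related (high vs. low coherence) activity in the dorsal pathway". The ventral limb follows: "whereas rTMS-V will enhance motion-related activity in ventral pathway, with little or no effect on motion task performance". The control is not described there.

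Section 4, Study 2 explains how the dorsal and ventral placements are derived and then concludes: "Thus, Study 2 uses 3 spatial conditions for rTMS stimulation". The third is not named. Two readings are open.

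- **Vertex.** The motion task shared by all three studies is performed "while receiving rTMS to right MT or vertex". Table 2 of Study 1 and the site-by-state design of Study 3 both use vertex as the comparator, and the Study 1 analysis in section 12 treats vertex as the sham.
- **Another MT placement.** The Study 2 text says "Study 2 manipulates the location and orientation of the coil during rTMS of MT", and the overview in section 4 has similar wording. The targeting procedure in section 12 also computes an optimal MT placement for each participant.

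The Study 3 text states that Study 2 uses 5Hz only. The primary endpoint predicts that "1Hz vs. 5/10Hz rTMS will have inhibitory vs. excitatory effects on behavior" and on MT activity.

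The Study 2 part of section 12 covers tractography, functional connectivity and E-field modelling. It states no model or contrast for reaction time, accuracy or pathway activity, and no comparison of rTMS-D with rTMS-V.

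**The concern.** The objective of Study 2 is selective recruitment of one pathway. A comparison of rTMS-D with vertex changes two things at once: whether MT is stimulated at all, and how the coil is biased. If 5Hz stimulation of MT improves performance whatever the bias, as the primary endpoint's premise allows, rTMS-D beats vertex without any dorsal selectivity.

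The activity limbs have a similar weakness. The background on spatial targeting (section 3) says that rTMS also modulates regions connected to the stimulated site. A general MT effect that spreads could therefore raise dorsal activity under rTMS-D and ventral activity under rTMS-V, each relative to vertex, with no selectivity in either.

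The comparator thus decides what a positive secondary result means. If it is settled after the data are seen, the choice can follow the result.

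**Working it through.** **Inputs**
- 48 recruited per study, 20% drop-out, 38 completers (section 6).
- 3 conditions of 4 blocks of 20 trials, 10 s each (section 4, Study 2).
- Alpha 0.05, a medium effect and 30 subjects (section 12). This statement stands under Study 1; it gives no target power, sidedness or SD, and there is none for Study 2.
- Assumed: medium means a paired d of 0.5, with d = 0.3 as a smaller case; two-sided paired t-tests; equal correlations among the three conditions.

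**The plan's own figures.** 38 / (1 − 0.20) = 47.5, rounded up to 48, as stated. 3 × 4 × 20 = 240 trials, and 240 × 10 s = 2,400 s = 40 minutes, as stated. The unnamed condition holds 240 / 3 = 80 trials, one third of the data.

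**Step 1: rTMS-D versus vertex, general effect only.** Let the 5Hz MT effect be d under both rTMS-D and rTMS-V, with zero pathway effect. The test of rTMS-D against vertex then has noncentrality d√n on n − 1 degrees of freedom.
- n = 38, d = 0.5: 0.5 × √38 = 3.08, critical t = 2.03, probability of significance 85.1%.
- n = 38, d = 0.3: 0.3 × √38 = 1.85, probability 43.7%.
- n = 30: 75.4% at d = 0.5 and 35.5% at d = 0.3.

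**Step 2: the full performance pattern.** In the same scenario rTMS-V also beats vertex about 85% of the time at d = 0.5, which goes against the ventral prediction. Simulation with n = 38 and the SD of every paired difference set to 1 gives:

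| Assumed d | rTMS-D significant | rTMS-D significant, rTMS-V not |
|---|---|---|
| 0.5 | 85% | about 9% |
| 0.3 | 44% | about 17% |

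Both placements are therefore significant in about 85 − 9 = 76% of simulated studies at d = 0.5.

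**Step 3: the direct contrast.** Write the means as D = g + a, V = g + b, vertex = 0, where g is the shared MT effect and a and b are pathway effects.
- D − vertex = g + a, which is positive when a = 0 and g > 0.
- D − V = a − b, which is zero when a = b = 0, whatever g is.

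In simulation, rTMS-D significantly exceeds rTMS-V in about 2.5% of studies (about 5% two-sided) at every d tried.

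For activity, let the shared effect reach the dorsal regions with size g₁ and the ventral regions with size g₂. The interaction is (D dorsal − D ventral) − (V dorsal − V ventral). Its shared part is (g₁ − g₂) − (g₁ − g₂) = 0, even when the spread to the two pathways is unequal.

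**The case against.** **The endpoint is a dissociation, not only the dorsal limb.** This stands, and it limits the concern. A reader might infer from the 85% that any effective MT stimulation would be reported as a confirmed pathway effect. The documents do not support that: a purely general effect usually makes rTMS-V beat vertex too, which contradicts the ventral prediction for performance. The protection is incomplete, because a non-significant rTMS-V result would be read as little or no effect without a margin, and a difference in significance is not a test of the difference.

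**A general effect need not be equal across placements.** Section 3 says that the size and direction of TMS effects depend on coil position. So rTMS-V may truly do little, and the plan may keep that hypothesis. The equal-effect case is an assumption used to test the design, not a forecast.

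**The dorsal activity limb is not confirmed directly.** The primary prediction concerns reaction time and MT activity, not FEF or IPS. This stands: the activity limbs are exposed only if the effect spreads from MT.

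**Vertex is the natural reading, and a figure may show it.** Vertex is the likelier reading. The figures are not available and may depict the third condition. No available text defines it, and the vertex reading is the one that carries the problem.

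**An MT control would be better.** A reader might infer that vertex must be replaced. That does not follow. Nothing shows that the optimal placement in section 12 is neutral between pathways or distinct from the dorsal and ventral placements. If it drives MT harder than they do, the general effect does not cancel. Replacing vertex would also lose Study 2's within-subject off-target comparison; Study 3 compares MT with vertex in different participants and does not test the biased placements.

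**Conclusion.** The concern holds in a limited form. The control is undefined in the available text, vertex is its likeliest meaning, and separate contrasts with vertex do not isolate pathway selectivity. With a general effect alone and 38 completers, the dorsal performance limb is significant in about 85% of studies at d = 0.5 and 44% at d = 0.3. The full performance dissociation appears in about 9% and 17%, against about 2.5% for a direct contrast in the predicted direction.

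These figures rest on assumed effect sizes, an equal effect under both placements and equal correlations; the documents give only the word medium, and give it for Study 1. The direction does not depend on the exact size: any positive shared effect raises the chance that rTMS-D beats vertex and leaves D − V unchanged. If one placement drives MT more strongly than the other, D − V for performance would include that difference, so the direct contrast removes only the part that the two placements share.

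This should be corrected before the data are seen. It does not show that Study 2 is unsound or that the rTMS-V hypothesis is wrong.

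**What to change.** 1. In section 4, Study 2, state the site, coil position and orientation of the third condition, and bring the secondary endpoint, the section 4 overview and the shared motion task text into line with it.
2. If it is vertex, state that a contrast with vertex alone shows an effect of MT stimulation and does not by itself support a dorsal or ventral pathway claim.
3. In section 12, Study 2, pre-specify as the test of the pathway claim the within-subject rTMS-D versus rTMS-V contrast for performance, and the condition (rTMS-D, rTMS-V) by pathway (dorsal, ventral) interaction for motion-related activity. Keep the contrasts with control as supporting results.
4. Keep the rTMS-V hypothesis. An MT control is optional.

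The cost is protocol and SAP wording, a slightly longer analysis and a narrower claim from the vertex contrasts. The number of conditions, blocks and participants does not change.
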